22 EXIT VISIT

The categorical variables to be described are, N and (%):

- Reason for study exit
- Please explain why the investigator withdrew the subject
- Please specify the reason

23 PRIMARY OBJECTIVE

The primary objective of the study is to evaluate the safety profile of JPS within the scope of its intended purpose, when used according to the manufacturer IFU on a representative population of subjects and users.

In order to fulfill this objective, the safety profile of JPS will be assessed by the following endpoints:

- percentage (%) of subjects with at least one serious/not serious adverse event certainly related or possibly related to JPS (primary endpoint) at device removal follow-up (up to 18 months according to site's standard practice).
- percentage (%) of Medical Device Deficiencies (MDDs) at device removal follow-up (up to 18 months according to site's standard practice).

23.1 ADVERSE EVENTS

The categorical variables to be described are, N and (%) and Clopper-Pearson confidence intervals will be shown at 95.2% as well:

- Implants with at least one adverse event
- Implants with at least one serious adverse event
- Patients with at least one adverse event
- Patients with at least one serious adverse event

23.1.1 ADVERSE EVENTS DESCRIPTION

The categorical variables to be described are, N and:

- Adverse Event Description by implant
- Adverse Event Description by patient
- The detailed description of the AE for each Adverse Event Description by implant

23.1.2 ADVERSE EVENTS SERIOUSNESS

The categorical variables to be described are, N and:

- The detailed description of the AE for each: Seriousness / Not seriousness

23.1.3 ADVERSE EVENTS POTENTIALLY LINKED TO JPS MD?

The categorical variables to be described are, N and (%) and Clopper-Pearson confidence intervals will be shown at 95.2% as well:

- According to the investigator, is this AE potentially linked to JPS Medical Device? by implants
- According to the investigator, is this AE potentially linked to JPS Medical Device? by patients
- Is this AE linked to a Medical Device Deficiency? by implants
- Is this AE linked to a Medical Device Deficiency? by patients

23.1.4 ADVERSE EVENTS LIST

A list with adverse events collected and its characteristics will be shown.

23.2 MEDICAL DEVICE DEFICIENCIES (MDD)

The categorical variables to be described are, N and (%) and Clopper-Pearson confidence intervals will be shown at 95.2% as well:

- Implants with at least one MDD
- Patients with at least one MDD

23.2.1 MEDICAL DEVICE DEFICIENCIES (MDD) TYPES AND DESCRIPTION

The categorical variables to be described are, N and (%):

- Types of MDD by implant
- Types of MDD by patient
- For each type of MDD description will be shown by implant

23.2.2 MEDICAL DEVICE DEFICIENCIES (MDD) RESULTED IN AN ADVERSE EVENT FOR THE PATIENT

The categorical variables to be described are, N and (%) and Clopper-Pearson confidence intervals will be shown at 95.2% as well:

- Did this MDD resulted in an Adverse Event for the patient? by patient
- Did this MDD resulted in an Adverse Event for the patient? by implant

23.2.3 MEDICAL DEVICE DEFICIENCIES (MDD) LIST

A list with MDD collected and its characteristics will be shown.

24 SECONDARY OBJECTIVES

The secondary objective of the study is to evaluate the clinical performance of JPS within the scope of its intended purpose, when used according to the manufacturer IFU on a representative population of subjects and users.

In order to fulfill these objectives the clinical performance of JPS will be assessed by the two following efficacy endpoints:

- percentage (%) of subjects that reached a satisfactory bone consolidation according to investigator's opinion;
- percentage (%) of subjects that maintained bone correction alignment according to investigator's opinion until device removal.

24.1 SATISFACTORY BONE CONSOLIDATION

The categorical variables to be described are:

- Number of Implants that reached a satisfactory bone consolidation according to investigator's opinion in any visit
- Number of patients that reached a satisfactory bone consolidation according to investigator's opinion in any visit or implant

The descriptive statistic (Mean, SD, Median, Q₁, Q₃, Min, Max) will be shown for the following continuous variable:

- Time to full consolidation from surgery (months), per implant, considered at the first visit in which the answer is "Yes" in "Has been reached a satisfactory consolidation?" variables. Calculated as date of first satisfactory consolidation minus date of surgery.

A list will be made to identify possible outliers from the "time to full consolidation from surgery" in order to verify if there are any. In case any outliers descriptive of "time to full consolidation from surgery" will be repeated without the outlier data.

A list with satisfactory bone consolidation variables will be shown.

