5.1 Background Information

Principles of bone fixation through plating systems

Plating systems are treatment options for bone fixation, indeed they are intended to provide bone fragments stabilization in case of bone fracture or osteotomy. Fixation works by blocking movements that would prevent the normal biological process of callus formation and consolidation. Excessive movement would otherwise increase the incidence of delayed union or nonunion. The very same principle is exploited when surgical fusion of bone fragments is sought, for example in joint arthrodesis or after surgical osteotomies performed to correct a limb deformity.

The JPS is a complete plating system designed to address the specific demands of advanced deformity and trauma reconstruction of the lower extremities in pediatric population and small stature adults. The system is intended for internal fixation and stabilization of fractures, osteotomies, mal-unions and non-unions of long bones of the lower limb.

Indications (as per IFU)

The JPS is intended for internal fixation and stabilization of fractures, osteotomies, mal-unions and non-unions of long bones of the lower limb.

The JPS is indicated for internal fixation and stabilization of femoral and tibial fractures, osteotomies, mal-unions and non-unions. Indications include:

- Varus, valgus, rotational and/or shortening osteotomies
- Femoral neck and/or peritrochanteric fractures
- Proximal and distal metaphyseal fractures
- Pathological and impending pathological fractures

Use of the JPS JuniOrtho Plating System™ is indicated in pediatric (excluding newborns) and small stature adult patients.

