6.2 Secondary Objectives

The secondary objective of the study is to evaluate the clinical performance of JPS within the scope of its intended purpose, when used according to the manufacturer IFU on a representative population of subjects and users.

In order to fulfill these objectives the clinical performance of JPS will be assessed by the two following efficacy endpoints:

- percentage (%) of subjects that reached a satisfactory bone consolidation according to investigator's opinion;
- percentage (%) of subjects that maintained bone correction alignment according to investigator's opinion until device removal.

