10.2 Description Event by Event

10.2.1 V0: Screening and Baseline

Prospective patients who meet the eligibility criteria will be enrolled in the study. Patients who agree to enter the study must sign the approved Informed Consent Form. Consented patients will have performed assessments as outlined in this protocol.

During the screening the investigator will evaluate the eligibility of the patients, checking all inclusion and exclusion criteria. Only those patients who meet all inclusion and exclusion criteria will be enrolled in the study. For each JPS implant a unique case number will be assigned (ID), and reported in the eCRF. Considering that each patient can contribute for more than one JPS implant: one patient can have more than one ID. In the eCRF the IDs are linked to the first ID assigned to the same patient by the clinical site. The patients not enrolled for non compliance will be considered as screening failures and will not be entered in the eCRF. Only for the enrolled patient, the Investigator will collect the demographic data and the medical history of the patient including information concerning the limb to be treated with JPS (baseline) such as the radiographic images and clinical examination.

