24.2 MAINTAINED BONE CORRECTION

This analysis will be performed for cases that have indicated: Deformity Correction.

The categorical variables to be described are:

- Number of Implants that according to the investigator is the level of correction maintained until last visit performed
- Number of Patients that according to the investigator is the level of correction maintained until last visit performed

A list with maintained bone correction variables will be shown.

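### SAP 24.1 counts any later Yes as consolidation without regard to an intervening reoperation, so a rescue with the JPS retained counts as JPS success in both rows, and a JPS re-plating does so in the patient row

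*SAP*

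**What the plan says.** Protocol 6.2 defines the endpoint as the "percentage (%) of subjects that reached a satisfactory bone consolidation according to investigator's opinion". Protocol 12.3.1 and the synopsis name it the primary efficacy endpoint. None of these places gives a time point or mentions reoperation.

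SAP 24.1 turns it into two counts:

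- Implant row: "Number of Implants that reached a satisfactory bone consolidation according to investigator's opinion in any visit".
- Patient row: "Number of patients that reached a satisfactory bone consolidation according to investigator's opinion in any visit or implant".

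It also summarises time from surgery to consolidation per implant, taken at the first visit with a Yes. The question is asked at the first control, at the bone consolidation visit and again at device removal (SAP 19.1, 20.1, 21.1), with answers No, Partially or Yes. SAP 13 defines evaluable implants by the screening criteria alone, so nothing that happens after surgery changes a case's status.

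On the unit of analysis, Protocol 10.2.1 says "For each JPS implant a unique case number will be assigned (ID), and reported in the eCRF" and adds that "one patient can have more than one ID", the IDs being linked to the patient's first one. Protocol 5.1 states: "The JPS is indicated for internal fixation and stabilization of femoral and tibial fractures, osteotomies, mal-unions and non-unions". A JPS re-plating for non-union can therefore meet the indication and enter as a further case.

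**The concern.** The endpoint is meant to describe how well JPS holds the bone until it unites. SAP 24.1 records instead that the bone was at some point rated as united, whatever further surgery came first. A delayed union that is grafted or re-screwed around the retained plate, and then rated Yes at removal, scores the same as one that healed under the original fixation.

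Such courses are foreseeable. Protocol 5.1 describes fixation as protection against delayed union and non-union, Protocol 7.3 allows for clinical complications that alter the timing of removal, and Protocol 11.1.2 lists surgical intervention among the seriousness criteria. SAP 24.1 uses none of this.

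The study is intended to confirm the benefit/risk ratio and support the CE mark under the MDR. A performance percentage that does not fall when a failure is rescued with the plate in place does not isolate the performance of the device.

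**Working it through.** **Inputs.** 30 subjects (Protocol 12.2). Clopper-Pearson intervals at 95.2% (SAP 14), so α = 0.048. SAP 24.1 has no target, threshold or sample size, so there is no planned figure to reproduce. The documents give no reoperation rate. I assume k = 1, 2 or 3 affected patients of 30, one index implant each, with every bone eventually rated Yes.

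**Formula.** For x successes in n, the lower limit is the α/2 = 0.024 quantile of Beta(x, n − x + 1). When x = n this reduces to 0.024^(1/n). For 30/30 it is 0.024^(1/30) = 0.883.

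**Case A: reoperated with the JPS retained.** There is one ID, which ends in Yes. The SAP rule gives 30/30 in both rows whatever k is.

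| k | SAP rule (lower limit) | Rescued cases counted as not reached (lower limit) |
|---|---|---|
| 1 | 30/30 = 100% (88.3%) | 29/30 = 96.7% (82.6%) |
| 2 | 30/30 = 100% (88.3%) | 28/30 = 93.3% (77.8%) |
| 3 | 30/30 = 100% (88.3%) | 27/30 = 90.0% (73.3%) |

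Each such case adds 1/30 = 3.3 percentage points to both rows. Its time to consolidation is still counted from the original surgery to the Yes that followed the rescue.

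**Case B: JPS removed and re-plated with JPS under a new ID.** Follow-up lasts until JPS removal (Protocol 7.3), and consolidation is asked at removal (SAP 21.1). The first ID therefore closes as No or Partially and stays in the denominator. The second ID adds one case and one Yes.

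| k | SAP patient row | SAP implant row | Index implants only |
|---|---|---|---|
| 1 | 30/30 = 100% | 30/31 = 96.8% | 29/30 = 96.7% |
| 2 | 30/30 = 100% | 30/32 = 93.8% | 28/30 = 93.3% |
| 3 | 30/30 = 100% | 30/33 = 90.9% | 27/30 = 90.0% |

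The implant row shifts by 0.1 point at k = 1 and 0.9 point at k = 3. The patient row is overstated by 3.3 points per case, because a Yes on the second implant overrides the failure of the first.

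**The case against.** The strongest reply is that this is inferred from silence. No sentence says that consolidation after rescue counts; the rating is the investigator's opinion, and an investigator might not answer Yes for a rescued bone. That is fair as to intent. But the question asks whether the bone has consolidated, not whether it did so under JPS alone, and a Yes at any visit is all the rule requires.

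A second reply is that failures are not hidden. Adverse events are tabulated by implant and by patient and listed in full (SAP 23.1 to 23.1.4). Consolidation is tabulated visit by visit, and SAP 24.1 lists its variables. This stands: the failure is missing from the performance figure, not from the report.

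Third, other plates, external fixators and nails on the same bone are not permitted (Protocol 9.2.2), and deviations are reported and discussed (Protocol 14.5). This also stands in part, but neither document says whether a case that later receives such a device is dropped, kept or counted as reached.

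Fourth, the endpoint is descriptive and serves a secondary objective, so no stated decision rule changes.

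Three stronger readings are tempting, and the documents do not support them:

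- **Re-plating hides failures in the implant row.** It does not. The first ID stays there as not consolidated (Case B).
- **Extra IDs dilute the safety result.** The primary safety endpoint is per subject, so its denominator cannot grow. Only the additional per-implant percentage in Protocol 12.3.2 can move: one related event goes from 1/30 = 3.3% to 1/31 = 3.2%.
- **SAP 24.2 has the same fault.** Its rule is "Number of Implants that according to the investigator is the level of correction maintained until last visit performed". That is not an any-visit rule, and it may already require that no correction was lost in between.

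**Conclusion.** The point holds for SAP 24.1 in two places. Consolidation after a reoperation that leaves the JPS in place counts as success in both rows, and the time summary runs through it. A JPS re-plating under a new ID turns a failed first fixation into a success in the patient row only. The patient row matters most, because the protocol endpoint is a percentage of subjects.

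The overstatement is 3.3 points per affected patient in 30. With 1 to 3 rescued with the JPS retained, the report would read 100% (lower limit 88.3%) instead of 96.7% to 90.0% (lower limits 82.6% to 73.3%). These figures assume that all rescued bones heal and are rated Yes. The number affected is itself an assumption and may be zero. This is a change that should be made to the SAP; it does not bear on the primary safety endpoint.

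**What to change.** In SAP 24.1, before the final analysis:

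1. Define success as a Yes with no prior unplanned further operation on the JPS-treated bone for loss of fixation, loss of correction, or delayed or non-union, and with no Protocol 9.2.2 device added. Count all other implants as not reached, also in the time-to-consolidation summary.
2. Judge the patient row on the index implant(s), so that a JPS re-implantation on the same bone cannot convert a failure. Flag such repeat cases in the implant row.
3. Show the present any-visit counts beside the new ones as supportive figures.
4. Identify the cases from the AE/SAE form and the linked IDs. The item asking whether further surgery is recommended is not a suitable source: it records a recommendation rather than an operation, and SAP 17.2, 19.2, 20.2 and 21.3 list it only under a Yes to the correction question. Protocol 11.1.2 has the causative event recorded rather than the procedure, so the event descriptions will need to be read case by case. Treated bone and side (SAP 16.6) help to identify same-bone repeats.

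The cost is SAP wording, one derived variable and possibly a slightly lower efficacy percentage. No new visit is needed.

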PROCEDURES	
One selected site that is experienced in the treatment of pediatric and adult patients with bone deformities and fractures, where the usage of JPS is already part of the normal clinical practice, will participate in this study. Investigator will provide data for a maximum of 40 JPS implant cases satisfying inclusion and exclusion criteria (predicted drop out rate is 10%) that will contribute for at least 30 cases treated by JPS (note that some patients may contribute for more than one JPS case, according to how many JPS implants were received).
 
For retrospective study cohort, who has previously had JPS implanted and follow-up assessment and JPS removal is done, the investigators shall purely collect clinical data from the medical record of the subjects, concerning the screening criteria, the surgery (MD application) and 4 following events: hospital discharge, first post-application control, bone consolidation assessment and device removal. Data from patients' observation are collected according to the site standard-of-care.
 
Patients, who are prospectively enrolled in the study and have undergone JPS implantation, will have follow-up assessments, as described on Table 10.2, or until patient withdrawal.

[figure not shown]
	
The patient data will be systematically collected by the investigator in eCRF. As per CIP, the subjects will not undergo additional visit nor non-invasive, invasive or burdensome procedures additional to those performed under the normal clinical practice.
					
OBJECTIVES	
The objectives of this study are to assess:
 
 - the safety profile (primary objective) - the clinical performance (secondary objective) 
of the JPS within the scope of its intended purpose, when used according to the manufacturer IFU on a representative population of subjects and users.
					
SAFETY ENDPOINTS	
The safety profile of JPS will be assessed by the following safety endpoints:
 
 - Percentage (%) of subjects with at least one serious/not serious adverse event certainly related or possibly related to JPS (ADEs) (primary safety endpoint) at device removal follow-up (up to 18 months according to site's standard practice); - Percentage (%) of MD Deficiencies (MDDs) at device removal follow-up (up to 18 months according to site's standard practice). 					

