12.3 Safety and Clinical Performance endpoints

12.3.1 Efficacy endpoints

The clinical performance of JPS will be assessed by the following efficacy endpoints:

- percentage (%) of subjects that reached a satisfactory bone consolidation (primary efficacy endpoint);
- percentage (%) of subjects that maintained bone correction alignment until device removal (secondary efficacy endpoint).

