16.2 ENROLMENT VISIT

16.3 DEMOGRAPHIC DATA BY PATIENT

The categorical variables to be described are, N and (%):

- Number of implants by patient
- Gender (Male / Female)
- Medical conditions by patient (Yes / No):
 - Transient synovitis
 - Septic arthritis
 - Juvenile idiopathic arthritis
 - Cerebral palsy
 - Slipped Capital Femoral Epiphysis SCFE
 - Developmental Dysplasia of the Hip DDH
 - Blounts Disease
 - Neurogenic Hip Dysplasia
 - Ligamentary laxity
 - LeggCalvPerthes disease
 - Spina bifida
 - Down Syndrome
 - Chromosomal aberration
 - Other, specify (other medical conditions will be shown). The sponsor will give an elaboration of the open text with the correct number of other conditions inserted.
- Number of Medical conditions, considering other as one
- History of cardiovascular disease (Yes / No)
- History of diabetes (Yes / No)
- Family history of disease: Renal disease (Yes / No)
- Family history of disease: Deafness (Yes / No)
- Family history of disease: Cardiomyopathy (Yes / No)

- Family history of disease: Encephalopathy (Yes / No)
- Family history of disease: Diabetes Mellitus (Yes / No)
- Family history of disease: Hypertension Cardiovascular disease (Yes / No)
- Family history of disease: Thrombosis (Yes / No)
- Family history of disease: Malignancy (Yes / No)

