16.6 DIAGNOSIS & X-RAY IMAGES BY IMPLANT

The categorical variables to be described are, N and (%):

- The patient was treated for (Deformity Correction / Fracture). In case of fracture the following variables will be described:
 - The date of fracture is available?
 - Type of fracture (neck fracture / Pertochanteric fracture / Methaphyseal fracture / PathologicalImpending pathological fracture / Other (specify)).
- Treated bone (Distal Femur / Distal Tibia / Proximal Femur / Proximal Tibia)
- Body side (Left / Right)
- Body side (Only Left / Only Right / Both). A new variable will be generated based on original variable body side. For implants with only left, with only right and with both the variable "Treated bone (Distal Femur / Distal Tibia / Proximal Femur / Proximal Tibia)" will be described separately.
- Plane(s) of deformity: Frontal
- Plane(s) of deformity: Horizontal
- Plane(s) of deformity: Sagittal
- A new variable will be generated with the different combinations based on Plane(s) of deformity variables. (Frontal / Horizontal / Sagittal / Frontal-Horizontal / Frontal-Sagittal / Horizontal-Sagittal, etc...)
- Intended correction: Varus correction
- Intended correction: Valgus correction
- Intended correction: Rotational correction
- Intended correction: Shortening correction
- Intended correction: Extension correction
- A new variable will be generated with the different combinations based on Intended correction variables.

The descriptive statistic (Mean, SD, Median, Q₁, Q₃, Min, Max) will be shown for the following continuous variables:

- Degree Varus
- Degree Valgus
- Degree antecurvature

The categorical variables to be described are, N and (%):

- Was a software used during pre-planning ? (Yes / No)

- Did the patient refer pain at the affected limb before JPS application? (Not at all / A little bit / Moderately /Quite a bit /Extremely)
- In case of previous question is not equal to 'Not at all' VAS will be described
- In case of previous question is not equal to 'Not at all' VAS Pain Score according to the patient will be described
- Preoperative AP projection X-Ray
- Preoperative ML projection X-Ray

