24.3 WEIGHT BEARING GRADE

The categorical variables to be described are:

- Number of Implants that reached a Full weight-bearing (FWB) from surgery in any visit
- Number of Patients that reached a Full weight-bearing (FWB) from surgery in any visit or implant

The descriptive statistic (Mean, SD, Median, Q₁, Q₃, Min, Max) will be shown for the following continuous variable:

- Time to Full weight-bearing from surgery (months), per implant, considered at the first visit in which the answer is "Full weight-bearing (FWB)" in "Weight-bearing Protocol" variables. Calculated as date of the first visit of Full weight-bearing minus date of surgery.

A list will be made to identify possible outliers from the "time to full weight-bearing" in order to verify if there are any. In case any outliers descriptive of "time to full weight-bearing" will be repeated without the outlier data.

A list with Weight bearing grade variables will be shown.

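### SAP 24.1 scores a patient as consolidated if any one of their implants consolidates, so a patient with one healed and one unhealed bone is a full success in the subject-level primary efficacy percentage

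*SAP*

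**What the plan says.** Protocol 12.3.1 defines the endpoint per subject: "percentage (%) of subjects that reached a satisfactory bone consolidation (primary efficacy endpoint"). The Protocol Synopsis (Procedures) expects subjects with several implants: "note that some patients may contribute for more than one JPS case, according to how many JPS implants were received". Protocol 10.2.1 gives each implant its own ID, linked to the patient's first ID. Nowhere does the protocol say how two implants in one patient make a single subject-level outcome.

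The SAP also expects such patients. Section 16.3 tabulates "Number of implants by patient", and 16.6 derives "Body side (Only Left / Only Right / Both). A new variable will be generated based on original variable body side".

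The combining rule appears only in SAP 24.1, where a patient counts on the investigator's "opinion in any visit or implant". The line above it, for implants, refers to any visit and stops there, so the reference to implants was added for the patient count. Section 24.1 also plans the implant count and a listing of the consolidation variables. SAP 24.3 uses the same form for weight-bearing: "Number of Patients that reached a Full weight-bearing (FWB) from surgery in any visit or implant".

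**The concern.** Read as written, the rule takes each patient's best implant. A patient whose left femur healed and whose right femur did not is recorded as having reached consolidation, with nothing in the subject-level row to mark the difference. The any-visit part fits an endpoint about having reached consolidation and is not questioned. The any-implant part has no source in the protocol.

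The direction matters. In SAP 23.1, "Patients with at least one adverse event" lets one event in any implant count the patient, which is cautious for a harm. Applied to a benefit, the same any-implant logic is favourable. It can only raise the subject rate relative to requiring every implant to heal, and it can put the subject rate above the implant rate from the same data.

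At stake is how the named primary efficacy figure reads in a study meant to support the device's benefit-risk case and its continued CE marking.

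**Working it through.** The plan states no target, expected rate or power for consolidation, so there is no figure of its own to reproduce. The check compares scoring rules on the same patients.

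**Inputs from the documents.** Maximum 40 implant cases (Protocol Synopsis); 30 subjects as the calculated sample size (Protocol 12.2).

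**Assumed, because the documents do not give them.** At most two plates per patient; m patients with two plates; the same failure rate f (5% or 10%) for every implant; within-patient correlation rho of 0 or 0.5. Failure means the implant is never scored as satisfactorily consolidated at any visit.

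**A counted example.** Take 30 patients and 40 implants, 10 patients with two plates, and 2 of those 10 with one failed plate each.

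- SAP 24.1 rule: 30/30 = 100%.
- By implant: 38/40 = 95.0%.
- Every implant required: 28/30 = 93.3%.

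**Expected size.** For a two-plate patient, the probability that exactly one plate fails is d = 2f(1 − f)(1 − rho). Then:

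- P(at least one plate heals) = 1 − f + d/2
- P(both plates heal) = 1 − f − d/2

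The two rules lie equally far above and below the implant-level rate 1 − f, whatever the correlation. Over N = 40 − m patients, the any-implant rule exceeds the implant rate by m·d/(2N) and exceeds the all-implants rule by m·d/N.

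For m = 10, N = 30, f = 0.05, rho = 0: d = 2 × 0.05 × 0.95 = 0.095. The excess over the implant rate is 10 × 0.095/60 = 1.58 points, and over the all-implants rule 3.17 points. Direct check: (20 × 0.95 + 10 × 0.9975)/30 = 96.58% and (20 × 0.95 + 10 × 0.9025)/30 = 93.42%, either side of 95%.

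Results in percentage points, each range running from rho = 0.5 to rho = 0:

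| Two-plate patients (all patients) | f | Above implant rate | Above all-implants rule |
|---|---|---|---|
| 5 (35) | 5% | 0.3–0.7 | 0.7–1.4 |
| 5 (35) | 10% | 0.6–1.3 | 1.3–2.6 |
| 10 (30) | 5% | 0.8–1.6 | 1.6–3.2 |
| 10 (30) | 10% | 1.5–3.0 | 3.0–6.0 |
| 20 (20) | 5% | 2.4–4.8 | 4.8–9.5 |
| 20 (20) | 10% | 4.5–9.0 | 9.0–18.0 |

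**Chance that the rule matters at all.** The probability of at least one mixed patient is 1 − (1 − d)^m. With m = 10 this is 38% to 63% at f = 5% and 61% to 86% at f = 10%. If no patient has mixed results, the two subject-level rules give the same figure.

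**The case against.** The strongest reply is that the protocol prescribes no combining rule, so requiring every implant has no more textual support than accepting any. Half of the gap between the two rules is the downward shift of the stricter one. That stands, and the size is therefore stated against the implant rate. A reader might take the full 1.6–3.2 or 3.0–6.0 points as overstatement of the protocol's endpoint; the documents do not support that.

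A reader might also infer that a failed plate disappears from the report. It does not: the implant count is the adjacent line and a listing follows. In the counted example the reader would see 38/40 beside 30/30.

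Nor would a pass/fail conclusion change. The endpoint sits under the secondary objective, is descriptive, and has no threshold. The only stated hypothesis (Protocol 12.1) concerns safety. SAP 24.1 names no confidence interval, unlike the safety sections, so no comparison of limits is made here.

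The larger values in the table are remote. Twenty two-plate patients would mean 20 subjects, below the 30 of Protocol 12.2. A 5–10% rate of never consolidating by device removal is itself unsupported by the documents.

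The contrast with safety is only illustrative, since counting a patient on one event is the protocol's own definition for adverse events. Full weight-bearing is not a protocol efficacy endpoint, so 24.3 carries little weight.

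None of this gives the any-implant rule a basis in the protocol or removes its favourable direction.

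**Conclusion.** The point holds in a limited form. SAP 24.1 applies a best-implant rule to the protocol's subject-level primary efficacy percentage, and a patient with mixed results is scored as a full success. Under the central assumptions (40 implants, 30 patients, 10 with two plates), the expected lift over the implant rate is about 0.8–1.6 points at 5% implant failure and 1.5–3.0 points at 10%. Single-implant patients are unaffected, so the true size depends on how many patients have several implants and how many of those have mixed results. It is worth correcting because the rule moves a named endpoint in the favourable direction and the remedy is nearly free.

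**What to change.** In SAP 24.1, define by-patient success for the protocol endpoint as every evaluable implant of that patient reaching satisfactory consolidation, each at any visit. Add a row for patients with mixed results, beside the unchanged implant count and listing. If the any-implant count is kept, label it as such and do not present it as the protocol endpoint. Aligning 24.3 is optional, for consistency.

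The cost is a change to the SAP wording and a recode of eCRF data already linked by patient. The downside is that the subject-level rate may fall by the number of mixed patients. Because patients with more plates have more chances to fail, it will also tend to sit below the implant rate, so the two figures should be read together.
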